### **5.3.1.1.4. HBeAg Sero clearance**

Sero clearance of HBeAg is defined as a (quantitative) HBeAg level <LLOQ and is assessed for participants HBeAg positive at baseline only.

### **5.3.1.1.5. HBsAg and HBeAg Seroconversion**

Seroconversion of HBsAg is defined as having achieved HBsAg sero clearance (as quantitative HBsAg level <LLOQ) and appearance of anti-HBs antibodies, defined as a baseline anti-HBs (quantitative) <LLOQ and a post-baseline assessment  $\geq$ LLOQ.

Seroconversion of HBeAg is defined as having achieved HBeAg sero clearance (as quantitative HBeAg level < LLOQ) and appearance of anti-HBe antibodies, defined as a baseline anti-Hbe antibodies (qualitative) with a "NEGATIVE" result and a post-baseline assessment with "POSITIVE" result.

The seroconversion will only be assessed at the time points when the anti-HBs or anti-HBe antibodies assessment is available.

#### **5.3.1.1.6. Suppressed HBV DNA**

HBV DNA < LLOQ (HBV DNA detectable or HBV DNA TND) will be evaluated all time points when assessed after stopping all study interventions at the end of the consolidation phase and without restarting NA treatment.

HBV DNA < LLOQ (HBV DNA detectable or HBV DNA TND) will be also evaluated when assessed at all time points after stopping all study interventions (regardless when intervention was stopped) and without restarting NA treatment.

If the HBV DNA value at FU Week 12 is missing, the next available observation will be used. The next non-missing lab test no later than FU Week 24 will be imputed.

If the HBV DNA value at FU Week 24 is missing, the LOCF in conjunction with the next available observation imputation approach will be used. The available non-missing lab test closest to FU Week 24 which is no earlier/later than 12 weeks from the actual time point of interest (FU Week 12 and FU Week 36, respectively) will be imputed.

If the HBV DNA value at FU Week 36 is missing, the LOCF in conjunction with the next available observation imputation approach will be used. The available non-missing lab test closest to FU Week 36 which is no earlier/later than 12 weeks from the actual time point of interest (FU Week 24 and FU Week 48, respectively) will be imputed.

If the HBV DNA value at FU Week 48 is missing, the LOCF approach will be used with the condition that no value earlier than FU Week 36 may be carried forward.

For all other time points, HBV DNA will be analyzed as observed case without imputation.

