- a. All follow up study visits are to be scheduled relative to the last dose of JNJ 3989/PegIFN α2a. An unscheduled visit can be performed upon the investigator's discretion, in case of HBV DNA elevations, ALT elevations, other signs of worsening of liver disease, or for any other reason during follow up.
- Participants who withdraw consent during follow up will be offered an optional safety follow up visit.
- c. Participants who discontinue study intervention early will have an early WD visit and will enter follow up unless they withdraw consent. Participants who withdraw consent during study intervention will be offered an optional safety follow up visit to occur on the day of consent withdrawal. For the optional safety follow up visit, assessments are at the investigator's discretion and could be similar to the early WD visit.
- d. Follow up Week 8, 16, 20, 28, 32, 40, and 44 visits are not required for participants who did not complete NA treatment at Follow up Week 2 and for participants who have restarted NA treatment during the follow up period, provided that their HBV DNA and ALT values are stable.
- e. In between study visits, participants will take NA orally at home and will bring their NA with them to each study visit. At study visits, NA should be taken on site. PegIFN α2a should be administered weekly, preferably in the evening by self injection. If desired, participants can also choose to have the weekly administration of PegIFN α2a performed on site irrespective of the time of day. PegIFN α2a should preferably be administered in the evening prior to the sparse PK visit, or alternatively in the morning of the visit on site.

- f. No JNJ 3989/PegIFN α2a will be administered or dispensed during follow up. Administration/Dispensation of NA is only applicable for participants who could not stop NA treatment, or for those who met the NA re treatment criteria. In between study visits, participants will take NA at home and they will bring their NA treatment with them to each study visits, the NA treatment should be taken on site.
- g. If the NA treatment completion criteria are met at consolidation Week 12, treatment with NA will be completed at FU Week 2.
- h. Complete physical examination, including body weight, skin examination, and other body systems.
- i. Vital signs include supine SBP, DBP, pulse rate, and body temperature.

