### **5.2.2.1.3. Last Observation Carried Forward (LOCF)**

The third approach to handle missing data is based on the LOCF principle (single imputation). If the HBsAg value at FU Week 24 is missing and NA treatment has not been restarted, then LOCF in conjunction with the next available observation imputation will be applied. The available non-missing HBsAg value closest to the time point which is no earlier/later than 12 weeks prior/after to the FU Week 24 time point will be used. Participants who do not have data within the analysis window of  $\pm 12$  weeks around the FU Week 24 assessment will be defined as non-responders.

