### **5.3.1.1.3. HBsAg Sero clearance**

Sero clearance of HBsAg is defined as a (quantitative) HBsAg level <LLOQ. HBsAg sero clearance may be achieved prior to the time point assessed but must be observed at the given week of interest.

HBsAg sero clearance will be evaluated over all time points when assessed.

HBsAg sero clearance will be also evaluated when assessed at all time points after stopping all study interventions (regardless when intervention was stopped) and without restarting NA treatment.

If the HBsAg value at FU Week 12 is missing, the next available observation will be used. The next non-missing lab test no later than FU Week 24 will be imputed.

If the HBsAg value at FU Week 24 is missing, the LOCF in conjunction with the next available observation imputation approach will be used. The available non-missing lab test closest to FU Week 24 which is no earlier/later than 12 weeks from the actual time point of interest (FU Week 12 and FU Week 36, respectively) will be imputed.

If the HBsAg value at FU Week 36 is missing, the LOCF in conjunction with the next available observation imputation approach will be used. The available non-missing lab test closest to FU Week 36 which is no earlier/later than 12 weeks from the actual time point of interest (FU Week 24 and FU Week 48, respectively) will be imputed.

If the HBsAg value at FU Week 48 is missing, the LOCF will be used with the condition that no value earlier than FU Week 36 may be carried forward.

For all other time points, sero clearance will be analyzed as observed case without imputation.

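### SAP 5.3.1.1.6 and 5.3.1.1.3 can fill a missing FU Week 12, 24 or 36 value from a visit after NA restart, so NA-suppressed HBV DNA can count as off-treatment suppression

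*SAP*

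**What the plan says.** SAP 5.3.1.1.6 evaluates HBV DNA <LLOQ "after stopping all study interventions at the end of the consolidation phase and without restarting NA treatment". A parallel evaluation covers participants regardless of when intervention stopped, again without NA restart. Missing values are handled by time point:

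- At FU Week 12, forward only: "If the HBV DNA value at FU Week 12 is missing, the next available observation will be used", with the limit "The next non-missing lab test no later than FU Week 24 will be imputed".
- At FU Week 24, either direction: "The available non-missing lab test closest to FU Week 24 which is no earlier/later than 12 weeks from the actual time point of interest".
- At FU Week 36, either direction: "The available non-missing lab test closest to FU Week 36 which is no earlier/later than 12 weeks from the actual time point of interest".
- At FU Week 48: backward carry-forward only, from no earlier than FU Week 36.

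SAP 5.3.1.1.3 has the same scheme for HBsAg, beginning "If the HBsAg value at FU Week 12 is missing, the next available observation will be used". None of these rules mentions NA.

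The primary-endpoint fill rule in SAP 5.2.2.1.3 is different. It applies only "If the HBsAg value at FU Week 24 is missing and NA treatment has not been restarted".

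**The concern.** The protocol's account of potential benefits (2.3.1.2) states that NA brings HBV DNA close to or below the LLOQ. A value taken after NA restart therefore says little about control off treatment. If it stands in for a missing off-treatment value, a participant who lost suppression and went back on NA can be tabulated as suppressed without NA. The error runs in one direction, towards response.

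The SAP shows that it regards this condition as necessary. It states it for the primary endpoint, and Section 2.4 ends the off-treatment period when NA re-treatment starts. The secondary fill rules refer to neither. As a result, HBsAg at FU Week 24 has two fill rules in the same SAP, one with the NA condition and one without.

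**Working it through.** **1. Does the endpoint definition close the gap?** A restart before the target time point is already excluded. What remains is a restart after the target and before the later visit that supplies the value. The summaries in SAP 5.3.2.1.2 and 5.3.2.1.4 give no date for the restart condition, except in the additional restricted-denominator summary, where restart is checked only up to the time point of interest. A later restart passes that check.

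**2. FU Week 24 record.** Inputs from SAP Table 2(c): target day 169, window days 156–183. Inputs from the Protocol 1.3.2 follow-up schedule, with ±4 days: FU Week 20 is day 141, so 137–145; FU Week 28 is day 197, so 193–201. I take SAP follow-up days and protocol follow-up days as aligned.

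- Day 137: HBV DNA at or above LLOQ, off NA.
- Days 156–183: no HBV DNA result in the analysis data.
- Day 170: NA restarted at the investigator's discretion, which Protocol 6.6.2 allows.
- Day 193: HBV DNA <LLOQ, on NA.

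Distances to target: 169 − 137 = 32 days; 193 − 169 = 24 days. The closest test is the on-NA value, so it replaces an observed off-NA value that showed no suppression. The restart on day 170 falls after target day 169, so the participant has not restarted before the time point.

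If the time point is read as the whole window, the restart must fall after day 183. An on-NA value up to day 200 would still be closer than day 137 (200 − 169 = 31, against 32). The same structure applies at FU Week 36.

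**3. FU Week 12 record.** The window is days 72–99 and the fill is forward only. The record needs no value on days 72–99, a restart after day 99, and no HBV DNA result in the analysis data before that restart. Protocol 1.3.2, footnote d, then waives FU Weeks 16 and 20 "for participants who have restarted NA treatment during the follow up period, provided that their HBV DNA and ALT values are stable". The next value can be FU Week 24, on NA, which is the latest the rule allows.

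**4. FU Week 48.** The fill is backward only, so a restart before the supplying visit is also a restart before the target. The endpoint definition already excludes it.

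**5. Size.** The only related figure in the plan is the exact 90% CI for 15/30, given as 0.339–0.661. Clopper-Pearson gives 0.3389–0.6611, so it reproduces. By the same method, for one misclassified participant:

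| Denominator | With NA condition | As written |
|---|---|---|
| 33 (planned Cohort 2) | 0/33 = 0% (90% CI 0–8.7%) | 1/33 = 3.0% (0.2–13.6%) |
| 30 (expected with data) | 0/30 = 0% (0–9.5%) | 1/30 = 3.3% (0.2–14.9%) |
| 1 (restricted to those off NA) | 0/1 | 1/1 |

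The last row uses the rationale in SAP Amendment 4, which reports one participant who met the completion criteria and stopped NA at consolidation Week 12.

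**The case against.** The best case against is that the rule seldom bites. Restart on HBV DNA grounds requires a value above 100,000 IU/mL, or increases confirmed at least 4 weeks apart, and Protocol 6.6.2 sets weekly or every-other-week re-testing above 20,000 or 2,000 IU/mL. A virologic relapser therefore produces off-NA results before restart, and those will usually be the next or closest test. This stands, and it is why the records above need a restart on other grounds (discretion, liver signs, HBeAg seroreversion) or a local result that did not reach the analysis data. Protocol 6.6.2 lets local results be recorded in the CRF and/or source documents.

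A reader might infer that anyone who misses FU Week 12, relapses and restarts at Week 13 is miscounted. That does not follow. Week 13 is day 13 × 7 + 1 = 92, inside the FU Week 12 window of days 72–99. Under SAP 2.1.3 the relapse result becomes the Week 12 value and nothing is imputed.

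It can also be said that the NA condition is implied by the endpoint wording, by Section 2.4, and by Protocol 9.4.1.2, which says that missing secondary data may be handled much as for the primary endpoint. That is a fair reading of intent, and nothing shows that the sponsor means to use on-NA values. But the fill rules are what will be programmed, and the one dated check stops at the target.

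**Conclusion.** The fill rules for FU Weeks 12, 24 and 36 are wrong as written, with a small expected effect: about one participant, 3.0 percentage points at N = 33. This assumes that the planned Cohort 2 size is the denominator, that the one participant reported off NA belongs to that cohort, and that an infrequent record occurs. Participants who stopped earlier could add to this in the analysis that ignores when intervention stopped.

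Two stronger readings are not supported. The first is that the main efficacy results are at risk. The primary LOCF rule carries the NA condition, the protocol's follow-up secondary endpoints on HBsAg and HBV DNA are at 48 weeks, where only backward fill applies, and the affected tables are descriptive. The second is that HBsAg seroclearance is inflated in the same way. Protocol 2.1 notes that very few patients on NA lost HBsAg, so for 5.3.1.1.3 the change is mainly for consistency. The move from 0/1 to 1/1 is arithmetically correct but describes a single participant and should not be read as a large bias.

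**What to change.** Add one sentence to SAP 5.3.1.1.6 and, for consistency, to 5.3.1.1.3: a value may be used for imputation only if it was obtained before any NA restart, using the off-treatment period of Section 2.4; if NA was restarted and no such value exists in the allowed window, the participant is a non-responder at that time point. In the FU Week 24 record above, the day 137 value would then be used and the participant would count as not suppressed.

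The cost is two sentences and one date comparison in the derivation. No figure in the documents changes, no new data are needed, and the rule then matches the SAP's own rule for the primary endpoint.

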#### **5.3.1.1.7. Thresholds Based on HBsAg, HBeAg, HBV DNA and Multiple Markers**

Thresholds for **HBsAg values**:

- <1000 IU/mL
- <100 IU/mL
- <10 IU/mL
- <1 IU/mL
- <0.05 IU/mL

Thresholds for **HBsAg decreases from baseline**:

- $\geq 0.3 \log_{10}$  IU/mL
- $\geq 0.5 \log_{10}$  IU/mL
- $\geq 1 \log_{10}$  IU/mL

- $\geq 2 \log_{10}$  IU/mL
- $\geq 3 \log_{10}$  IU/mL
- $\geq 4 \log_{10}$  IU/mL

Thresholds for **HBeAg** values (assessed for participants HBeAg Positive at baseline only):

- $< 100$  IU/mL
- $< 10$  IU/mL
- $< 1$  IU/mL
- $< \text{LLOQ}$  (0.11 IU/mL)

Of note, seroclearance of HBeAg is defined as (quantitative) HBeAg<LLOQ.

Thresholds for **HBeAg** decreases from baseline (assessed for participants HBeAg Positive at baseline only):

- $\geq 0.3 \log_{10}$  IU/mL
- $\geq 0.5 \log_{10}$  IU/mL
- $\geq 1 \log_{10}$  IU/mL
- $\geq 2 \log_{10}$  IU/mL
- $\geq 3 \log_{10}$  IU/mL

Thresholds for **HBV DNA** values:

- $< \text{LLOQ}$  for target detected and not detected
- $< \text{LLOQ}$  for target not detected
- $< \text{LLOQ}$  for target detected
- $< 60$  IU/mL
- $< 100$  IU/mL
- $< 200$  IU/mL
- $< 1000$  IU/mL
- $< 2000$  IU/mL
- $< 20000$  IU/mL

Thresholds for **HBV DNA** decreases from baseline:

- $\geq 1 \log_{10}$  IU/mL
- $\geq 2 \log_{10}$  IU/mL
- $\geq 3 \log_{10}$  IU/mL
- $\geq 4 \log_{10}$  IU/mL

- $\geq 5 \log_{10}$  IU/mL

### 5.3.1.1.8. Virologic Breakthrough

HBV virological breakthrough is defined as having a confirmed on-treatment HBV DNA increase by  $>1 \log_{10}$  from nadir level (lowest level reached) in participants who didn't have on-treatment HBV DNA level below the lower limit of quantification (LLOQ) or a confirmed on-treatment HBV DNA level  $>200$  IU/mL in participants who had on-treatment HBV DNA level below the lower limit of quantification (LLOQ). Confirmed HBV DNA increase/level means that the criterion should be fulfilled at 2 or more consecutive time points or at the last observed on-treatment time point. On-treatment will be defined as the time period in which the participant receives any of the study interventions (including NA).

In addition, participants who experience a virologic breakthrough followed by on-treatment biochemical flare will be evaluated.

### 5.3.1.1.9. Flares

The criteria based on blood markers/lab tests for each of the flare types are defined as below.

a) **Virologic flare** is defined as follows:

Virologic flare will be assessed only for those participants who are off-treatment and had HBV DNA  $<$  LLOQ at the last observed time point on all study treatments.

The start of a confirmed virologic flare is defined as the first date of two consecutive visits with HBV DNA  $> 200$  IU/mL. The end date of the same confirmed virologic flare is defined as the first date when HBV DNA value returns to  $\leq 200$  IU/mL or the date of NA treatment restart, whichever comes first. Each virologic flare will be categorized based on the confirmed (i.e., two consecutive values) peak HBV DNA above any of the three thresholds within the start and end date of that flare as follows: 20,000 IU/mL 2,000 IU/mL and 200 IU/mL

- 1 (Yes) = confirmed\*\* HBV DNA  $>$  peak threshold.
- 0 (No) = at least one off-treatment HBV DNA measurement available and not meeting the criteria of confirmed HBV DNA  $>$  peak threshold.
- 2 (Not applicable) = no off-treatment HBV DNA quantitative measurements available.

b) **Off-treatment Biochemical flare** is defined as follows:

The start date of a confirmed off-treatment biochemical flare is defined as the first date of two consecutive visits with ALT and/or AST  $\geq 3x$  ULN and  $\geq 3x$  nadir (i.e., lowest value observed up to the time point of meeting the biochemical flare criteria) while the participant does not receive any of the study interventions. The end date of the same off-treatment biochemical flare is defined as the first date when there is a 50% reduction from the peak ALT and/or AST level &  $< 3x$  ULN.

- 1 (Yes) = confirmed\*\* ALT and/or AST  $\geq 3x$  ULN and  $\geq 3x$  nadir (i.e., lowest value observed during off-treatment period up to the time point of meeting the biochemical flare criteria)
- 0 (No) = otherwise

c) **On-treatment Biochemical flare** is defined as follows:

The start date of a confirmed on-treatment biochemical flare is defined as the first date of two consecutive visits with ALT and/or AST  $\geq 3x$  ULN and  $\geq 3x$  nadir (i.e., lowest value observed up to the time point of meeting the biochemical flare criteria) while the participant receives any of the study interventions. The end date of the same on-treatment biochemical flare is defined as the first date when there is a 50% reduction from the peak ALT and/or AST level &  $< 3x$  ULN, regardless of stopping the study interventions.

- 1 (Yes) = confirmed\*\* ALT and/or AST  $\geq 3x$  ULN and  $\geq 3x$  nadir (i.e., lowest value observed on-treatment period up to the time point of meeting the biochemical flare criteria)
- 0 (No) = otherwise

d) **Clinical flare** is defined as follows:

A clinical flare occurs either when a virologic flare and biochemical flare overlap in time or when a biochemical flare starts within 4 weeks following the end of a virologic flare. The start date of a clinical flare is defined as the minimum start date of the virologic flare and the biochemical flare. The end date of a clinical flare is defined as the maximum end date of the virologic flare and biochemical flare, i.e., the later date between HBV DNA returns to  $\leq 200$  IU/mL and 50% reduction from the peak ALT and/or AST level &  $< 3x$  ULN .

- 1 (Yes)= confirmed\*\* HBV DNA  $>$  peak threshold and confirmed\*\* ALT and/or AST  $\geq 3x$  ULN and confirmed\*\*  $\geq 3x$  nadir (i.e., lowest value observed during off-treatment period up to the time point of meeting the flare criteria).
- 0 (No) = otherwise

\*\* Confirmed means that the criterion should be fulfilled at 2 or more consecutive time points or at the last observed time point.

The virologic and clinical flares will be assessed only off-treatment, while biochemical flares will be identified on treatment and off treatment, respectively. On-treatment virologic flares are described as virologic breakthrough in Section 5.3.1.1.8. On-treatment will be defined as the time period in which the participant receives any of the study interventions. Off-treatment will be defined as the period after stopping all study interventions (including NA). In addition, the proportion of subjects with off-treatment virologic flares, ALT and clinical flare for subjects who met NA treatment completion criteria and stopped NA will be shown.

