## 8.3.6.2. Intervention-emergent ALT/AST Elevations

Elevated liver enzyme activity can be triggered by the underlying HBV disease as well as by the study intervention.

Management of intervention-emergent ALT/AST elevations is presented graphically in Section 10.6, Appendix 6, Intervention-emergent ALT/AST Elevations and is described below.

Any intervention-emergent elevation of ALT and/or AST ≥3x ULN and ≥3x nadir (ie, lowest value during study participation) should trigger an assessment of confounding factors (alcohol intake, change in concomitant medication, and comorbidities) and should trigger a confirmatory study visit to repeat laboratory testing of AFP, ALT, AST, ALP, bilirubin (total and direct), INR, albumin, and HBV DNA. Additional tests should be considered based on clinical judgement (Refer to Section 10.6, Appendix 6, Intervention-emergent ALT/AST Elevations). The confirmatory visit should be scheduled as soon as possible, preferably within 7 days of the receipt of the initial ALT/AST results. In case the repeat laboratory testing shows an isolated ALT/AST elevation (ie, with stable albumin, bilirubin [total and direct], and INR) the participant may continue study intervention. In case of confirmed ALT elevation >1,000 U/L and ≥3x the baseline value, JNJ-3989 and PegIFN-α2a should be discontinued unless dynamics of the ALT elevation are indicating improvement towards resolution of the flare. In both cases, NA treatment should be continued. The participant will be monitored (laboratory testing of ALT, AST, ALP, bilirubin [total and

direct], INR, albumin, and HBV DNA) on a weekly basis until ALT and AST levels have returned to <5x ULN and HBV DNA is <20,000 IU/mL.

If the ALT and/or AST level is  $\ge 3x$  ULN and  $\ge 3x$  nadir and is associated with any of the following laboratory results or clinical symptoms:

- INR  $\geq$ 1.5, OR
- direct bilirubin >1.5x ULN, OR
- serum albumin <3.0 g/dL, OR
- ascites, hepatic encephalopathy, or liver-related symptoms (eg, severe fatigue, nausea, vomiting, right upper quadrant pain in the absence of an alternative medical explanation), OR
- other indication of reduced liver function

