#### **Definitions of Terms**

ALT/AST nadir Lowest ALT/AST value during study participation

End-of-study intervention

(EOSI)

Time of the last administration of study intervention

HBsAg seroclearance HBsAg negativity based on the assay used

HBsAg seroconversion HBsAg negativity and anti-HBs antibody positivity

Intervention cohort Cohorts of adult participants with chronic hepatitis B virus infection who receive a

specific study intervention within this Platform study, and in whom the efficacy and

safety of that intervention is evaluated

Study intervention Prior to Protocol Amendment 6: JNJ-73763989, JNJ-56136379, NA (tenofovir

disoproxil) and PegIFN-α2a

As of Protocol Amendment 6: JNJ-73763989, NA (tenofovir disoproxil) and

PegIFN-α2a

Study intervention phase 36-week induction phase plus 12-week consolidation phase

Virologic breakthrough Confirmed on-treatment HBV DNA increase by >1 log10 IU/mL from nadir or

confirmed on-treatment HBV DNA level >200 IU/mL in participants who had HBV

DNA level <LLOQ of the HBV DNA assay

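### SAP 5.3.1.1.9 gives two conflicting ALT/AST nadirs for the same biochemical flare, so the start-date rule and the yes/no flag can disagree

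*SAP*

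**What the plan says.** All biochemical flares require ALT and/or AST of at least 3x ULN and at least 3x nadir. SAP 5.3.1.1.9 describes the nadir in two ways.

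- Start date, off-treatment (b) and on-treatment (c): the "lowest value observed up to the time point of meeting the biochemical flare criteria", with no limit to a treatment period.
- 1 (Yes) line in (b): the "lowest value observed during off-treatment period up to the time point of meeting the biochemical flare criteria".
- 1 (Yes) line in (c): the "lowest value observed on-treatment period up to the time point of meeting the biochemical flare criteria".
- 1 (Yes) line in (d), clinical flare: the "lowest value observed during off-treatment period up to the time point of meeting the flare criteria".

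The protocol has one definition. Appendix 1 (Section 10.1, Definitions of Terms) gives the ALT/AST nadir as "Lowest ALT/AST value during study participation". Section 8.3.6.2 uses it for the management trigger: "Any intervention-emergent elevation of ALT and/or AST ≥3x ULN and ≥3x nadir (ie, lowest value during study participation". Section 4.2 applies the same nadir to weekly visits in the follow-up phase.

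SAP 5.3.2.1.7 then asks for the incidence of each flare type on and off treatment and for the number of flares per participant. It does not say whether these come from the dated episodes or from the yes/no lines.

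**The concern.** Flare frequency is a secondary endpoint and a safety description. Two rules for one event mean that a participant can have a flare start date and a flag of No. They also mean that two programmers following the same section can produce different tables. A participant can meet the protocol's follow-up monitoring threshold and still be tabulated as having no flare.

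The direction is fixed. A minimum taken over part of the record cannot be lower than the minimum over the whole record. With the confirmation rule held constant, the flag can therefore only lose flares relative to the start-date rule.

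The case at risk is ALT that is already rising when treatment stops, and this design can produce it. The NA completion criteria (Protocol 6.6.1) allow ALT up to just under 3x ULN. NA is stopped at FU Week 2, so the first scheduled off-treatment ALT is normally FU Week 4. If that value is already raised, it becomes the reference for the off-treatment flag.

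**Working it through.** The point concerns a definition, so the plan has no figure to reproduce. All ALT values below are assumed for illustration; none comes from the documents.

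**When the rules disagree.** Let N be the lowest value so far in the study and P the lowest value so far within the period (P ≥ N).

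- Start-date rule: ALT ≥ 3 ULN and ALT ≥ 3N.
- Flag: ALT ≥ 3 ULN and ALT ≥ 3P.
- They differ when max(3 ULN, 3N) ≤ ALT < 3P.

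If P is at or below 1x ULN, then ALT ≥ 3 ULN already implies ALT ≥ 3P and the rules agree. Disagreement therefore needs P above 1x ULN.

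**A case in U/L.** Take ULN 40, on-treatment nadir 20, FU Week 4 at 100, then FU Week 8 and a repeat at 250.

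- Start-date rule: 3 x 40 = 120 and 3 x 20 = 60. 250 passes both, so it is a flare.
- Flag: 3 x 100 = 300. 250 fails, so No.

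**How wide the gap is.** With N = 0.5x ULN, the flag misses peaks from 3x ULN up to, but not including, 3P:

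| Off-treatment nadir P (x ULN) | Missed peaks (x ULN) |
|---|---|
| 1.0 | none |
| 1.25 | 3 to 3.75 |
| 1.5 | 3 to 4.5 |
| 2.0 | 3 to 6 |
| 2.5 | 3 to 7.5 |
| 2.9 | 3 to 8.7 |
| 3.5 | 3 to 10.5 |

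**Full series.** The SAP footnote was applied to both rules: "Confirmed means that the criterion should be fulfilled at 2 or more consecutive time points or at the last observed time point". The start-date sentences mention only two consecutive visits, but A and B each have two consecutive qualifying visits, so their result does not depend on that. Values are x ULN.

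| Series | On treatment | Off treatment | On-treatment flare | Off-treatment, start-date rule | Off-treatment flag |
|---|---|---|---|---|---|
| A | 0.6, 0.5, 0.9, 1.8, 2.4 | 3.2, 4.8, 6.0, 2.0 | No | Yes | No (needs 3 x 3.2 = 9.6) |
| B | 0.6, 0.5, 0.7, 0.9, 1.2 | 1.8, 4.5, 5.0, 1.5 | No | Yes | No (needs 3 x 1.8 = 5.4) |
| C | 0.6, 0.5, 0.7, 0.9, 1.2 | 1.8, 5.6, 6.0, 1.5 | No | Yes | Yes |
| D | 0.6, 0.5, 0.7, 0.8, 0.9 | 1.0, 3.2, 3.5, 1.0 | No | Yes | Yes |
| E | 0.6, 0.5, 0.5, 0.6, 0.5 | 0.5, 0.6, 4, 5 | No | Yes | Yes |
| F | 0.6, 0.5, 3.2, 3.6, 4.0 | 5, 6, 3, 1 | Yes | Yes | No |

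If the flags are counted, A and B appear in neither category. C, D and E are found by both rules. F is lost off treatment but still counted as an on-treatment flare. With one study-wide nadir, flag and start date agree in every series.

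**On-treatment flag.** SAP 2.4 starts the on-treatment period at first drug intake, so the flag in (c) leaves out pre-dose values and the start-date rule does not. The same condition applies: every on-treatment value so far must exceed 1x ULN, with a lower value before dosing.

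**The case against.** **A period-specific nadir may be intended.** All three flags use one, and SAP 5.3.1.2.1 separates on-treatment, follow-up and whole-study nadirs for HBsAg, HBeAg and HBV DNA. This stands in part: one period-specific nadir used in both places would also end the conflict. But the SAP gives no reason for it, does not use it for the start dates, and would then depart from the protocol definition.

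**The start-date sentence might be read as limited to the period.** Its wording is "lowest value observed up to the time point of meeting the biochemical flare criteria) while the participant does not receive any" of the interventions. The closing clause falls outside the parenthesis that defines the nadir, so it qualifies the visits. It does not restrict the nadir.

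**The events stay visible.** This stands. The protocol's study-wide nadir drives confirmatory and weekly visits (8.3.6.2, 4.2), and post-treatment ALT above 5x ULN triggers weekly retesting (6.6.2); 250/40 is 6.25x ULN. ALT/AST elevation is an adverse event of special interest (SAP 6.1.3), worst laboratory grades include unscheduled values (6.2.1), and the plots show all ALT data. The independent panel adjudicates each flare, although SAP 3.2 refers to this same section for the definition. A reader might infer that a safety event would be hidden; the documents do not support that. What can change is a cell in a descriptive table.

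**The reported incidence might be inferred to be understated.** SAP 5.3.2.1.7 does not establish that the flag is what is counted. It also wants the number of flares per participant, which a yes/no flag cannot supply and dated episodes can. The supportable statement is that the source is unspecified.

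**Conclusion.** The conflict is real on the wording alone: two nadirs for one flare in (b) and (c), the period-limited one repeated in (d), and a protocol definition that agrees with the start-date rule. It is a minor point.

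Size: the flag misses only flares for which the period nadir is above 1x ULN and the peak stays below three times that nadir. It would be tempting to say that it misses every flare already rising at the stop. Series C and F show otherwise: a higher peak is still flagged, and a rise that met the criterion before the stop is counted as on-treatment.

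Few participants are exposed off treatment. The Amendment 4 rationale in the SAP reports one who met the completion criteria and stopped NA; others could come off NA only by another route, such as premature discontinuation. With a denominator of one, a single disagreement would move the off-treatment result for that subgroup between 0/1 and 1/1. The on-treatment split could in principle reach any treated participant, but how often cannot be judged from the documents.

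The conclusion rests on the literal text of 5.3.1.1.9 and on assumed ALT series. The virologic flare in (a) depends on HBV DNA alone and uses no nadir, so three of the four definitions are affected.

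**What to change.** In SAP 5.3.1.1.9 (b), (c) and (d), use one nadir for both start date and flag: the lowest ALT/AST value during study participation up to that time point, as in Protocol Appendix 1. Leave (a) unchanged. Add a sentence to 5.3.2.1.7 stating that flare incidence and counts are derived from that single rule.

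If a period-specific nadir is preferred, it should be used for both start date and flag, with a reason and a note that it departs from the protocol.

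The cost is SAP wording and one derivation. No new data and no protocol change are needed.
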